1 PROTOCOL SYNOPSIS

Vertos MEDICAL		PROTOCOL SYNOPSIS
Title: The MOTION™ Study		
Purpose:	[REDACTED]	
Study Design: Prospective, multicenter, randomized controlled clinical study examining functional improvement in lumbar spinal stenosis (LSS) patients with neurogenic claudication who are treated with the MILD procedure plus conventional medical management (CMM), Study Group, compared to those treated with CMM alone, as the control.		
Objective: To evaluate long-term functional improvement following treatment with MILD plus CMM, compared to CMM alone in subjects with painful LSS and neurogenic claudication.		
Number of Subjects: Approximately 150 subjects	Number of Study Centers: Up to 20 centers in US	
[REDACTED]		
Randomization:		

Control Group: CMM alone (without MILD). [REDACTED]

Treatment Group: MILD plus CMM.

Entry Criteria

Inclusion Criteria:

1. Age 50-80
2. Patients experiencing neurogenic claudication symptoms for at least 3 months duration.

[REDACTED]

[REDACTED]

[REDACTED]

[REDACTED]

b. Radiologic evidence of LSS with unilateral or bilateral ligamentum flavum $\geq 2.5\text{mm}$ in thickness² confirmed by pre-op MRI or CT performed within 12 months of baseline visit.

3. Patients with comorbid conditions commonly associated with spinal stenosis, such as osteophytes, facet hypertrophy, minor spondylolisthesis (Grade I without instability), foraminal stenosis, and/or disk protrusion may be included unless the medical monitor and the treating physician has determined that the condition is too advanced.
4. Stable opioid intake with no change during 30 days prior to enrollment.
5. Available to complete all follow-up visits.

Exclusion Criteria:

1. ODI Score < 31 (0-100 ODI Scale).
2. NPRS Score < 5 (0-10 NPRS Scale).
3. Lumbar epidural steroid injections during eight weeks prior to study enrollment.
4. Baseline analgesic medication greater than 90 milligram morphine equivalent (MME) per day.
5. Prior surgery at the same treatment level.
6. Previously received interspinous spacer at the same treatment level.
7. Previously received intradiscal procedure at the same treatment level.
8. Previously received vertebral augmentation procedure at the same treatment level.
9. Previously received the MILD procedure at the same treatment level.
10. Received radiofrequency ablation at the same or the adjacent levels within 6 months prior to study enrollment.
11. History of spinal fractures with current related pain symptoms.
12. Grade II or higher spondylolisthesis.
13. Motor deficit or disabling back and/or leg pain from causes other than LSS neurogenic claudication (e.g. acute compression fracture, metabolic neuropathy, or vascular claudication symptoms, etc.).
14. Unable to walk \geq 10 feet unaided before being limited by pain. In this context, 'unaided' means without the use of a cane, walker, railing, wall, another person or any other means of walking assistance.
15. Previously randomized and/or treated in a similar clinical study.
16. Epidural lipomatosis (if it is deemed to be a significant contributor of canal narrowing by the medical monitor and the treating physician).
17. On (or pending) Workman's Compensation or in active litigation or known to be considering litigation associated with back pain.

Statistical Analysis:

Continuous data will be summarized using descriptive statistics: mean, standard deviation, median, minimum and maximum. Categorical variables will be summarized using frequency counts and percentages. For events that can occur more than once in a single subject (e.g., adverse events), the percentage will be based on subjects experiencing the event, and both patient and event counts will be reported. All hypothesis testing will be performed using a two-sided test at a 0.05 level of significance or a one-sided test at a 0.025 level of significance.

[figure not shown]
[figure not shown]
[figure not shown]
[figure not shown]
[figure not shown]
[figure not shown]
[figure not shown]
Data will be analyzed on an Intent-to-Treat basis, under which analyses will be performed according to randomized assignment irrespective of the treatment actually received.

Consented patients who withdraw consent prior to randomization, or who are found not to meet the inclusion/exclusion criteria prior to randomization will not be included in the Intent-to-Treat population. The primary analysis will consist of all available data evaluated under Intent-to-Treat principles, referred to in ICH E9 ("Statistical Principles for Clinical Trials") as the *full analysis set*. An "as treated" analysis will also be performed which will report results based on treatment actually received.

2 STUDY DESIGN RATIONALE AND COMPLIANCE

2.1 STUDY DESIGN RATIONALE

This is a prospective, multi-center, randomized controlled clinical study examining functional improvement in lumbar spinal stenosis (LSS) patients with neurogenic claudication who are treated with the MILD procedure plus conventional medical management (CMM) compared to those treated with CMM alone, as the control.

[figure not shown][figure not shown]
Figure 1: MILD Device Kit

3.1.1 MILD Procedure

The MILD procedure is performed minimally-invasively under fluoroscopic image guidance through a dorsal approach to the spine. At the beginning of the MILD procedure, patients are placed in the prone position with a slight flexion, not to exceed 20 degrees. Following epidurography, partial decompression is performed through the removal of tissue and bone at the symptomatic level confirmed with correlated MRI and clinical findings. Pre and post procedure imaging with contrast (epidurogram) will be performed with the patient in the same position for both. All procedures will be conducted in accordance with the product labeling and indications for use.

3.2 CONVENTIONAL MEDICAL MANAGEMENT (CMM)

CMM involves treatment with one or more conservative therapies that are commonly used for treatment of LSS with neurogenic claudication. The study investigators at each site will determine what CMM is appropriate for each patient.

4 STUDY OBJECTIVE

The key objective of this study is to evaluate long term functional improvement following treatment with MILD plus CMM, compared to CMM alone in subjects with painful LSS and neurogenic claudication. Comprehensive safety will also be evaluated and reported.

5 STUDY DESIGN

This study is a prospective, multicenter, randomized controlled clinical study examining functional improvement (defined by improvement in ODI) in LSS patients with neurogenic claudication who are treated with MILD plus CMM compared to those treated with CMM alone, as the control.

5.1 NUMBER OF SITES AND SUBJECTS

To ensure that the study is adequately powered, up to 150 subjects will be enrolled at approximately 20 sites. All sites will be located in the United States. Each participating investigational site will be allowed to enroll up to 20 subjects who meet all study eligibility criteria. Additional subjects may be enrolled with sponsor approval.

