6 STUDY PROCEDURE

6.1 PATIENT SELECTION AND BASELINE VISIT

Selection begins with a screening process when the patient is examined by their physician. Once the investigator has determined that the patient is potentially eligible for treatment in the study, the consent should be reviewed with the patient, questions answered, and the patient should be asked to sign the Informed Consent document. The eligibility of a patient for treatment in this study will be determined after all enrollment criteria have been satisfied.

completed, all enrollment criteria are met and an informed consent signed, will the patient be officially enrolled into the study.

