9 GENERAL STATISTICAL METHODOLOGY

All subjects who are treated will be evaluated for safety regardless of whether or not the procedure is aborted or the patient withdraws prior to the completion of all post-treatment evaluations.

Continuous data will be summarized using descriptive statistics: mean, standard deviation, median, minimum and maximum. Categorical variables will be summarized using frequency counts and percentages. For events which can occur more than once in a single subject (e.g., adverse events), the percentage will be based on subjects experiencing the event, and both patient and event counts will be reported. All hypothesis testing will be performed using a two-sided test at a 0.05 level of significance or a one-sided test at a 0.025 level of significance.

Data will be analyzed on an intent-to-treat (ITT) basis, under which analyses will be performed according to randomized assignment irrespective of the treatment actually received.

Consented patients who withdraw consent prior to randomization, or who are found not to meet the inclusion/exclusion criteria prior to randomization will not be included in the ITT population. The primary analysis will consist of all available data evaluated under ITT principles, referred to in ICH E9 (“Statistical Principles for Clinical Trials”) as the full analysis set. An as-treated analysis will also be performed for the primary efficacy endpoint which will report results based on treatment actually received irrespective of randomization.

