10.2 MEDICAL MONITOR (MM)

The MM will be an Individual who is knowledgeable in the appropriate disciplines and medical specialties pertinent to the disease state being evaluated in this clinical Study. The MM will be a qualified medical practitioner who has experience and training in the MILD device and procedure. During the course of the study, the MM will:

- Review all subject medical records, baseline imaging to confirm the diagnosis and the appropriate level(s), Measure the thickness of ligamentum flavum at the treatment level(s). Also, ensure that eligibility criteria are met prior to randomization.
- Monitor overall study safety.
- Approve patient enrollment including review of MRIs.
- Respond to patient safety related inquiries from members of the Clinical Team including, but not limited to: patient eligibility, prohibited medications or procedures, exclusionary medical history, adverse events, and protocol deviations that impact patient safety.
- Participate in protocol development and amendment review.

- Perform comprehensive periodic review and assessment of patient enrollment, study data and protocol compliance.
- Prepare and/or review SAE narratives if applicable.
- Ensure adequate documentation of safety decisions.
- Escalate safety events as necessary.
- Consult with other study advisors as needed for safety issues requiring additional input.
- Support publication of study results in peer-reviewed journal within 1 year of study completion.

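### Does a sample size worded as both a ceiling and an approximate target, with room for extra subjects, leave power and type I error unprotected?

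*Combined protocol and SAP*

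**What the plan says.** Three statements bear on the size of the trial.

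- Synopsis: "Number of Subjects: Approximately 150 subjects".
- Section 5.1, overall total: "To ensure that the study is adequately powered, up to 150 subjects will be enrolled at approximately 20 sites".
- Section 5.1, site cap and then the extension sentence: "Each participating investigational site will be allowed to enroll up to 20 subjects who meet all study eligibility criteria", followed directly by "Additional subjects may be enrolled with sponsor approval".

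Section 6.1 fixes when a subject counts as enrolled, in a sentence whose opening is missing from the public text: "completed, all enrollment criteria are met and an informed consent signed, will the patient be officially enrolled into the study". Section 9 leaves out of the ITT population anyone who withdraws consent, or is found ineligible, before randomization. It sets the level of testing as "a two-sided test at a 0.05 level of significance or a one-sided test at a 0.025 level of significance".

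Sections 10.1 and 10.2 give the study principal investigator and the medical monitor the same duty: "Perform comprehensive periodic review and assessment of patient enrollment, study data and protocol compliance". Section 13.6 reserves protocol amendments to the sponsor and, apart from changes that increase safety, requires IRB/EC approval before they are put into effect.

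Parts of the synopsis, its statistical paragraph and section 9 are redacted or appear only as figures that are not shown.

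**The concern.** Taken literally, a maximum cannot secure power: a trial that stopped at 100 would still comply with 5.1. The unit is enrolled subjects, while the analysis set is randomized subjects with data, so the analysed number could fall below 150 even before dropout. The extension sentence has no limit, trigger or timing. The arms are a procedure plus conventional management against conventional management alone, no blinding is described in the readable text, and two senior roles review study data periodically.

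Put together, this could mean enrollment being stopped early or prolonged by people who know how ODI is running by arm. Two things would then be at stake: the power implied by 150, and the 0.025 one-sided level of the primary test.

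**Working it through.** **Can 150 be reproduced?** No. Effect size, SD, power and dropout are not in the readable text. What 150 delivers can still be calculated. Inputs from the documents are 1:1 allocation (section 6.2), a difference in mean ODI improvement (section 9.1), and two-sided 0.05 or one-sided 0.025, which put the same probability in the upper tail (0.05 / 2 = 0.025).

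**Detectable effect with n = 75 evaluable per arm**, in SD units: d = (1.960 + z_power) × √(2/n), and √(2/75) = 0.1633.

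- 80% power: (1.960 + 0.842) × 0.1633 = 0.457
- 90% power: (1.960 + 1.282) × 0.1633 = 0.529

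**Cost of falling short.** Power = Φ(d/√(2/n) − 1.960). The effects below are assumptions.

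| Evaluable total | Loss from 150 | Power at 0.46 SD | Power at 0.53 SD |
|---|---|---|---|
| 150 | 0% | 80.4% | 90.1% |
| 135 | 10% | 76.2% | 86.8% |
| 127.5 | 15% | 73.8% | 84.9% |
| 120 | 20% | 71.2% | 82.7% |

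Example: at 0.46 SD and n = 75, Φ(0.46/0.1633 − 1.960) = Φ(0.857) = 80.4%. Ten subjects lost between enrollment and randomization (140 left) would take this to 77.7%, a drop of 2.7 points.

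The table does not show that the trial is short of subjects, because 150 may already allow for attrition. For instance, 0.50 SD at 80% power needs 126 evaluable subjects, and with 15% dropout that is 126 / 0.85 = 148.2, rounded up to 149 enrolled. The public text does not say which case applies.

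**Does the site cap settle the total?** No: 20 sites × 20 subjects = 400. The total of 150 therefore rests on its own sentence. The permission for additional subjects comes straight after the site cap, so it can be read as an exception for a fast-recruiting site that leaves the total alone.

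**Type I error if the total did rise.** Let Z₁ be the statistic at 150 and Z₂ the independent statistic from m added subjects. The final statistic is (√150·Z₁ + √m·Z₂)/√(150 + m), tested at 1.960. Results are from 4 million simulated null trials per setting, against a nominal one-sided 0.025.

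| Assumed extension rule | m = 15 | m = 30 | m = 50 | m = 75 |
|---|---|---|---|---|
| Test at 150, extend if not significant, retest | 0.032 | 0.035 | 0.037 | 0.039 |
| By-arm look at 100 decides extension, one final test (worst of the rules tried) | 0.027 | 0.028 | 0.029 | 0.030 |

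When the decision to extend is unrelated to the treatment effect, the result is 0.0251 (m = 50), so there is no inflation. Three unadjusted tests at 100, 150 and 200 would give 0.049. Every inflated figure needs a rule that the readable plan does not state.

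**Do the documents link data review to extension?** Sections 10.1 and 10.2 do not describe the review as comparative, by arm or concerned with efficacy. It belongs to the principal investigator and the medical monitor. Extra subjects need the sponsor's approval. No readable passage connects the two, and none describes an interim analysis or sample-size re-estimation.

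**The case for a change.** The best case for a change is that the wording defect is visible whatever the redactions hide. A ceiling and a target are different commitments: they disagree about stopping at 100 and about going to 155. The extension sentence is ambiguous on its face. No readable passage keeps by-arm ODI from those who review data or from the sponsor. Repair would take a few sentences and would forestall a later suggestion that the final number was chosen after seeing results.

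Much of this stands. The two wordings do differ, as do the site counts (a maximum of 20 in the synopsis, about 20 in 5.1), and the scope of sponsor approval is unstated. The enrolled-versus-randomized distinction is also real, but excluding subjects who leave before randomization is standard and does not bias the comparison.

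What does not stand is the step from loose wording to lost power or an inflated level. Absence of a written restriction on by-arm data is not evidence that enrollment will be steered by them. Nor can a power shortfall be asserted when the power inputs are unreadable. Writing in a firm 150 randomized, 75 per arm, could even be wrong if the underlying calculation counts enrolled or evaluable subjects.

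**Conclusion.** No change to the plan follows. The documents carry one sample size, 150, expressed loosely in two places. A sponsor who enrolls about that many and tests the primary hypothesis once, as the readable plan describes, reaches a sound conclusion.

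The power figures rest on assumed effects and dropout, so they show sensitivity rather than a deficit. Type I error stays at 0.025 unless extension depends on observed results by arm. Under the assumed rules with 15 to 75 added subjects it would be about 0.027 to 0.039, but no such rule appears. This reading assumes that the hidden statistical text contains no unadjusted interim test and that any rise in the total is not prompted by by-arm outcomes. If the final total moved materially from 150, the study report would need to say when and on what information that was decided.

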5.2 STUDY DURATION

Subjects who meet the inclusion / exclusion criteria may be enrolled

The screening/baseline visit and CMM procedures may take place at the investigator's medical office. MILD procedures will be performed at the treating ambulatory surgery centers or hospital. Subjects will be requested to return for follow-up at a location designated by research staff.

5.3 STUDY POPULATION

The study population will consist of subjects who are suffering from LSS with neurogenic claudication, and who meet the study selection and symptomatic diagnosis criteria.

5.4 SUBJECT INCLUSION/EXCLUSION CRITERIA

5.4.1 Inclusion Criteria

1. Age 50-80
2. Patients experiencing neurogenic claudication symptoms for at least 3 months duration.
[REDACTED]
3. Patients with comorbid conditions commonly associated with spinal stenosis, such as osteophytes, facet hypertrophy, minor spondylolisthesis (Grade I without instability), foraminal stenosis, and/or disk protrusion may be included unless the medical monitor and the treating physician has determined that the condition is too advanced.
4. Stable opioid intake with no change during 30 days prior to enrollment.
5. Available to complete all follow-up visits.

5.4.2 Exclusion Criteria

1. ODI Score < 31 (0-100 ODI Scale).
2. NPRS Score < 5 (0-10 NPRS Scale).
3. Lumbar epidural steroid injections during eight weeks prior to study enrollment.
4. Baseline analgesic medication greater than 90 milligram morphine equivalent (MME) per day.
5. Prior surgery at the same treatment level.
6. Previously received interspinous spacer at the same treatment level.
7. Previously received intradiscal procedure at the same treatment level.
8. Previously received vertebral augmentation procedure at the same treatment level.

9. Previously received the MILD procedure at the same treatment level.
10. Received radiofrequency ablation at the same or the adjacent levels within 6 months prior to study enrollment.
11. History of spinal fractures with current related pain symptoms.
12. Grade II or higher spondylolisthesis.
13. Motor deficit or disabling back and/or leg pain from causes other than LSS neurogenic claudication (e.g. acute compression fracture, metabolic neuropathy, or vascular claudication symptoms, etc.).
14. Unable to walk \geq 10 feet unaided before being limited by pain. In this context, 'unaided' means without the use of a cane, walker, railing, wall, another person or any other means of walking assistance.
15. Previously randomized and/or treated in a similar clinical study.
16. Epidural lipomatosis (if it is deemed to be a significant contributor of canal narrowing by the medical monitor and the physician).
17. On (or pending) Workman's Compensation or in active litigation or known to be considering litigation associated with back pain.

6 STUDY PROCEDURE

6.1 PATIENT SELECTION AND BASELINE VISIT

Selection begins with a screening process when the patient is examined by their physician. Once the investigator has determined that the patient is potentially eligible for treatment in the study, the consent should be reviewed with the patient, questions answered, and the patient should be asked to sign the Informed Consent document. The eligibility of a patient for treatment in this study will be determined after all enrollment criteria have been satisfied.

completed, all enrollment criteria are met and an informed consent signed, will the patient be officially enrolled into the study.

6.2 RANDOMIZATION

Subjects will be randomly assigned in equal number (1:1) to one of two treatment arms: 1) MILD procedure plus CMM or 2) CMM only.

Based on the information provided, the system will automatically generate the assigned treatment.

6.3 BASELINE ASSESSMENT

The following baseline assessments for all patients should be confirmed, completed and recorded in the medical records and on the appropriate Case Report Forms (CRFs) where applicable.

6.4 TREATMENT

Subjects will be treated with either MILD plus CMM or CMM alone based on randomization results.

6.4.1 MILD Procedure plus CMM

[figure not shown]
Physicians performing the MILD procedures are trained by Vertos on the proper labeling use of the MILD devices.

6.4.2 CMM Alone

Study investigator will determine the appropriate CMM therapy or therapies during the course of the study for subjects assigned to CMM Alone.

6.5 FOLLOW-UP PHASE

Subjects will complete all follow-up assessments listed below for each follow-up visit.

Term	Percentage
GMOs	~75%
Organic	~95%
Natural	~90%
Artificial	~65%
Organic	~95%
Natural	~90%
Artificial	~65%
Organic	~95%
Natural	~90%
Artificial	~65%
Organic	~95%
Natural	~90%
Artificial	~65%
Organic	~95%
Natural	~90%
Artificial	~65%

[figure not shown]
6.8 PAIN MANAGEMENT

In addition to CMM therapies, investigators may use narcotic and non-narcotic analgesics as needed by subjects according to the standard of care and if used for leg/back pain, shall be recorded at baseline and follow-up visits on the appropriate CRFs/eCRFs. [REDACTED]

6.9 STUDY SCHEDULE

At baseline, prior therapies will be documented, including frequency, duration, type of therapy
Documentation of analgesic use for the treatment of neurogenic claudication symptoms will
include frequency and dosage.

Device/Procedure-related unexpected complications and significant adverse events will be documented throughout the study period.

7 RISKS / BENEFIT ASSESSMENT

Both the MILD and CMM treatments carry risks of complications with the procedure and recovery. This study is considered an evaluation of marketed treatments, neither of which is a 'study' or 'investigation'.

MILD offers an option for LSS patients experiencing symptoms refractory to more conservative therapies. The Vertos MILD devices were cleared by the FDA for marketing in the USA in December 2006 under a 510(k). Procedural risks are reduced by physician training and by performing the procedure under direct fluoroscopic visualization. The MILD devices are radiopaque to provide ease of x-ray imaging and placement within the body during the procedure. Conformance with the product labeling and instructions for use will minimize these risks.

Potential risks and benefits for all therapies offered in this study are listed in Table 2.

Table 2: Procedure Risks and Benefits

Therapy	Benefits	Risks/Side Effects
---------	----------	--------------------

Physical Therapy (PT): Passive PT includes heat and cold therapy, Iontophoresis, tens, and ultrasound. Active PT includes exercise and stretching.¹³
	
 Non-surgical therapy that may provide relief of lower back and limb symptoms in patients with neurogenic claudication Muscle strengthening Correction of posture Reduction of inflammation Reduction of muscle spasms 	
 Fatigue Muscle ache Increase lower back Soreness Swelling Increase in localized pain Decrease in immunity due to the suppressive effect of the steroid

Nerve Blocks:
 
 Epidural steroid injection: Minimally invasive procedure that delivers steroids into the epidural space around spinal nerve roots to relieve pain.²⁰ Facet joint injection: Minimally invasive procedure using fluoroscopy for guidance and delivery of medication to relieve pain.¹⁴ Trigger point injection: Minimally invasive procedure used to treat painful areas of muscle that contain trigger points, or knots of muscle that form when muscles do not relax.¹⁵ Medial branch injection: Minimally invasive procedure in which an anesthetic is injected near small medial nerves connected to a specific facet joint.¹⁶ Sacroiliac joint injection: Minimally invasive procedure used either to diagnose or treat low back pain and/or sciatica symptoms associated with sacroiliac joint dysfunction.¹⁷ 	
 Potential relief of lower limb symptoms in patients with neurogenic claudication Shorter procedure time versus more invasive open or endoscopic surgical decompression Quick recovery following treatment, which may allow patients to return home same day as procedure No requirement for general anesthesia Less likelihood of significant complications versus open surgical procedures. No requirement for sutures 	
 Increase in localized pain Headaches or fever High blood sugar Decrease in immunity due to the suppressive effect of the steroid Increased intraocular pressure or cataracts Anxiety/sleeplessness Increased risks of osteoporosis Increased risk of avascular necrosis Exacerbation of diabetes Exacerbation of hypertension Numbness or slight weakness Allergic reaction, rash, itching Weight gain Increase in energy Soreness at injection site Bleeding Infection Worsening of pain symptoms Nerve or spinal cord damage or paralysis Shrinkage of fat under skin Death (in rare cases)

Radiofrequency ablation: Minimally invasive procedure that uses electrical current to heat a small area of nerve tissue for the purpose of
	
 Potential relief of lower limb symptoms in patients with low back pain 	
 Transient sunburn type pain Pain or discomfort around the area treated Numbness of skin covering the area treated


decreasing pain signals from that specific area.^{18,19}
	
 • Shorter procedure time versus more invasive open or endoscopic surgical decompression • Quick recovery following treatment, which may allow patients to return home same day as procedure • No requirement for general anesthesia • Less likelihood of significant complications versus open surgical procedures • No requirement for sutures 	
 • Worsened pain due to muscle spasm in the area treated • Permanent nerve pain • Allergies or reactions to medications used • Infection

MILD Procedure: Minimally invasive procedure that provides partial decompression through the removal of tissue and bone at the symptomatic level²⁰
	
 • Potential relief of lower limb symptoms in patients with neurogenic claudication • Shorter procedure time versus more invasive open or endoscopic surgical decompression • Quick recovery following treatment, which may allow patients to return home same day as procedure • No requirement for general anesthesia • Less likelihood of significant complications versus open surgical procedures • No requirement for sutures 	
 • Soreness at surgical site • Nerve injury (e.g., partial or complete paralysis, paresthesia, radiculopathy) • Injury to adjacent bony or soft tissue structures • Infection requiring surgical intervention • Inadequate pain relief • Allergic reaction and/or side effects from medications (e.g., constipation, gastrointestinal distress) • Dural tear or puncture • Bleeding (e.g. epidural hematoma)

